##### Old text:

[...]

- ~~Dispense alkaline hematin kit~~
- Dispense sanitary protection
- ~~Remind subjects to start collecting sanitary items on Day 50 of the TP2; collection to be continued until the end of this TP.  
Remind the subject to return all used sanitary protection items as soon as the bleeding episode has been completed.~~
- [...]
- Remind the subject to complete eDiary-based questionnaires until the next visit at home as required (UF-DSD, UF-DBD, MP) (see Sections 9.4.1 and 9.4.1.2.1)
- [...]

##### New text:

[...]

- Dispense AH kit and sanitary protection. Explain procedure for collection of sanitary protection items for measurement of menstrual blood loss.
- [...]
- Remind the subject to complete eDiary-based questionnaires until the next visit at home as required (UF-DSD, UF-DBD, MP) (see Sections 9.4.1 and 9.4.1.2.1)
- Remind the subject to return all used sanitary protection items as soon as the bleeding episode has been completed (but no later than 12 days from the start of the collection of the first item).
- [...]

### 15.1.2.11 Section 9.2.3.6 EoT visit

**Old text:**

[...]

- ~~Dispense alkaline hematin kit~~
- Dispense sanitary protection
- Collect used sanitary protection items, if they have not yet been provided to the site. ~~If a subject is continuing her treatment after the visit, remind her to continue collecting the used sanitary items until the end of her treatment and remind the subject to return them to the site as soon as bleeding episode has been completed.~~
- Remind the subject to return all used sanitary protection items as soon as a bleeding episode has been completed
- [...]

**New text:**

[...]

- [...]
- Dispense AH kit and sanitary protection. Explain procedure for collection of sanitary protection items for measurement of menstrual blood loss.
- Collect used sanitary protection items, if they have not yet been provided to the site.
- Remind the subject to continue collecting the used sanitary products during the follow-up
- Remind the subject to return all used sanitary protection items as soon as the bleeding episode has been completed (but no later than 12 days from the start of the collection of the first item).
- [...]

### 15.1.2.12 Section 9.4.3 Alkaline hematin method to assess HMB

**Old text:**

During the duration of the study, subjects will be required to use selected types of sanitary products provided (pads and/or tampons). During ~~specified periods~~ of the study, subjects need to collect their used sanitary products and return them to the study site as soon as the episode is completed to be sent to the central laboratory for analysis.

The AH method will be applied to measure MBL ~~during Screening and during the last 35 days of each treatment period~~. ~~Collection for 35 days at the end of each treatment period is chosen to avoid missing data for calculation of the primary endpoint (last 28 days of treatment) in cases where subjects stop treatment prematurely.~~

[...]

**New text:**

During the duration of the study, subjects will be required to use selected types of sanitary products provided (pads and/or tampons). During the entire duration of the study, subjects need to collect their used sanitary products and return them to the study site as soon as the bleeding episode is completed to be sent to the central laboratory for analysis.

The AH method will be applied to measure MBL from Screening onwards during the entire study.

[...]

### **15.1.2.13 Section 9.4.4 Ultrasound (efficacy) to assess uterine fibroids**

**Old text:**

[...]

The minimum source documentation will include printouts from the ultrasound machine showing the 3 largest fibroids. The printouts have to be labeled unambiguously, containing at least the study number, SID number, time point, and longest diameter of 3 largest fibroids.

For safety ultrasound procedures, see Section 9.6.3.6.

**New text:**

[...]

The minimum source documentation will include printouts from the ultrasound machine showing the 3 largest fibroids. The printouts have to be labeled unambiguously, containing at least the study number, SID number, time point, and longest diameter of 3 largest fibroids. It is also possible that the site has a CD with the ultrasound images available, when in the source the evaluation of the US images from the CD is available as well. The CRA should be able to review the data on the CD and compare the images with the evaluations in the source during the onsite monitoring visits.

Furthermore, if the ultrasound machine machine is SESAC (Site Electronic Source Assessment Checklist) conform, ie, GCP conform electronic data storage is possible, then no print out is needed.

For safety ultrasound procedures, see Section 9.6.3.6.

### **15.1.2.14 Section 9.6.1.1 Definitions**

**Old text:**

In a clinical study, an AE is any untoward medical occurrence (ie, any unfavorable and unintended sign [including abnormal laboratory findings], symptom or disease) in a patient or clinical investigation subject after providing written informed consent for participation in the study. Therefore, an AE may or may not be temporally or causally associated with the use of a medicinal (investigational) product.

[...]

**New text:**

In a clinical study, an AE is any untoward medical occurrence (ie, any unfavorable and unintended sign [including abnormal laboratory findings], symptom or disease) in a patient or clinical investigation subject after providing written informed consent for participation in the study. Therefore, an AE may or may not be temporally or causally associated with the use of a medicinal (investigational) product. Treatment emergent adverse event (TEAE) is defined as any event that occurred after the first study drug intake until the end of FUP.

[...]

**15.1.2.15 Section 9.6.3.1 Laboratory evaluations**

A footnote was added to Laboratory evaluations of hematocrit, hemoglobin, and ferritin stating that hemoglobin, hematocrit and ferritin are also efficacy variables.

**15.1.2.16 Section 9.6.3.3 Cervical smear**

**Old text:**

The cervical smear should be obtained with the gynecological examination at the visits shown in Table 9–1. It may be repeated once during the screening period if the results are abnormal (this repeat is not considered rescreening). If the cervical smear is repeated at Visit 2 (screening), it should be performed before the endometrial biopsy. The cervical smear at screening may be waived if a normal result has been documented in the subject's medical records within the previous 6 months. Subjects with ASCUS can be included in the study if they have an HPV deoxyribonucleic acid test that is negative for high-risk HPV.

**New text:**

The cervical smear should be obtained with the gynecological examination at the visits shown in Table 9–1. It may be repeated once during the screening period if the results are abnormal (this repeat is not considered rescreening). If the cervical smear is repeated at Visit 2 (screening), it should be performed before the endometrial biopsy. The cervical smear at screening may be waived if a normal result has been documented in the subject's medical records within the previous 6 months. Subjects with ASCUS can be included in the study if they have an HPV deoxyribonucleic acid test that is negative for high-risk HPV. As a guidance, cervical smear should only be repeated once in case of insufficient material.

**15.1.2.17 Section 9.7.1 Iron supplementation**

**Old text:**

If causes for anemia unrelated to HMB are suspected these subjects should not be enrolled.

Moderate anemia is defined as hemoglobin  $\leq 10.9$  g/dL (11). Iron supplementation should be offered to subjects with hemoglobin  $\leq 10.9$  g/dL consistent with local standards of practice and ~~the Centers for Disease Control and Prevention recommendation, ie, 50 to 60 mg of oral elemental iron (the approximate amount of elemental iron in one 325 mg tablet of ferrous sulfate) twice daily for 3 months for the treatment of iron deficiency anemia.~~ Iron supplementation will not be considered as study drug and should be documented as concomitant medication.

**New text:**

If causes for anemia unrelated to HMB are suspected these subjects should not be enrolled.

Moderate anemia is defined as hemoglobin  $\leq 10.9$  g/dL (11). Iron supplementation should be offered to subjects with hemoglobin  $\leq 10.9$  g/dL consistent with local standards of practice and at the investigator's discretion. Iron supplementation will not be considered as study drug and should be documented as concomitant medication.

**15.1.2.18 Section 9.7.3 Heavy menstrual bleeding / suspicious bleeding pattern**

**Old text:**

[...]

In case of suspicious bleeding pattern (eg, continuous spotting, unusually heavy bleeding) after the start of treatment, which does **not** resemble the subject's natural cycle or bleeding pattern, detected from the MP or UF-DBD, the subject should undergo immediate evaluation by the investigator.

Especially if during intake of the study drug and after the initial reduction of bleeding and/or onset of amenorrhea, any recording in the MP, or bleeding of an intensity of "mild" or worse occurs continuously for 10 days or more the subject should be instructed to contact the site for immediate evaluation.

[...]

**New text:**

[...]

In case of suspicious bleeding pattern (eg, continuous spotting, unusually heavy bleeding) after the start of treatment, which does **not** resemble the subject's natural cycle or bleeding pattern, detected from the AH, MP or UF-DBD, the subject should undergo immediate evaluation by the investigator.

Especially if during intake of the study drug and after the initial reduction of bleeding and/or onset of amenorrhea, any recording in the MP, worsened bleeding detected from the AH analysis, or bleeding of an intensity of "mild" or worse occurs continuously for 10 days or more the subject should be instructed to contact the site for immediate evaluation.

[...]

**15.1.2.19 Section 10.3.1 Variables**

**Old text:**

The primary efficacy variable will be calculated based on the alkaline hematin method. ~~Secondary and other variables related to menstrual blood loss will be calculated for the two methods, the alkaline hematin method and the menstrual pictogram, depending on the planned application of the methods.~~

**New text:**

The primary efficacy variable and secondary efficacy variables will be calculated based on the alkaline hematin method (unless otherwise specified). Other efficacy variables related to menstrual blood loss will be calculated based on the two methods, the alkaline hematin method and the menstrual pictogram.

### 15.1.2.20 Section 10.3.1.1 Primary efficacy variable

**Old text:**

[...]

Subjects who discontinue treatment ~~due to lack of efficacy, AEs, or~~ prior to completion of treatment Week 8 of the respective treatment period will be considered not having amenorrhea.

~~Further, based on scientific advice by FDA, subjects who did not adequately fulfill selection criteria or require fibroid surgery during study participation will be considered not having amenorrhea.~~

**New text:**

[...]

Subjects who discontinue treatment prior to completion of treatment Week 8 of the respective treatment period will be considered not having amenorrhea.

### 15.1.2.21 Section 10.3.1.2 Secondary efficacy variables

**Old text:**

The secondary efficacy variables are:

- ~~• Absence of bleeding (spotting allowed) during the last 28 days of the treatment; based on the UF-DBD~~
- ~~• Time to onset of controlled bleeding. Onset of controlled bleeding is defined by the first day, for which the menstrual blood loss for all subsequent 28-day periods up to the end of the treatment period is <80.00 mL~~
- HMB responder rate (percentage of subjects with blood loss <80.00 mL per 28 days and 50% reduction compared to baseline)

**New text:**

The secondary efficacy variables are:

- HMB response defined as blood loss <80.00 mL during the last 28 days of treatment and ≥50% reduction compared to baseline
- Time to onset of amenorrhea. Onset of amenorrhea is defined by the first day for which the menstrual blood loss for all subsequent 28-day periods up to the end of the treatment period is <2 mL.
- Time to onset of controlled bleeding. Onset of controlled bleeding is defined by the first day for which the menstrual blood loss for all subsequent 28-day periods up to the end of the treatment period is <80.00 mL.
- Absence of bleeding (spotting allowed) during the last 28 days of the treatment; based on the UF-DBD

### 15.1.2.22 Section 10.3.1.3 Other efficacy variables

#### Old text:

- Amenorrhea (yes/no), defined as MBL < 2 mL ~~during the last~~ 28 days of treatment (for treatment time/method not considered as primary variable)
- Volume of menstrual blood loss per 28 days
- Volume of menstrual blood loss per bleeding episode for the first, second, and if applicable third bleeding episode after the EoT
- Percentage of subjects with 50% reduction in menstrual bleeding per 28 days compared to baseline
- ~~• Time to onset of amenorrhea. Onset of amenorrhea is defined by the first day for which the menstrual blood loss for all subsequent 28-day periods up to the end of the treatment period is less than 2 mL.~~
- Time to start of bleeding after last study drug intake (assessed by the UF-DBD). If bleeding has to be induced, the subject's data will be censored at that time point for the induction.

[...]

- Change in CGI\_I scores compared to baseline.

#### New text:

[...]

- Treatment success rate defined as percentage of subjects who fulfill the criteria of HMB response (<80 mL, >50% reduction in menstrual blood loss as compared to baseline) and who have not been withdrawn from the study due to AEs, due to non-fulfillment of selection criteria (related to fibroid size or HMB at baseline) or due to fibroid surgery having been performed during the study.
- Amenorrhea (yes/no), defined as MBL < 2 mL per 28 days of treatment (for treatment time/method not considered as primary variable) HMB response defined as blood loss <80.00 mL and >50% reduction compared to baseline per 28 days of treatment (for treatment time/method not considered as secondary variable)
- Time to onset of amenorrhea. Onset of amenorrhea is defined by the first day for which the menstrual blood loss for all subsequent 28-day periods up to the end of the treatment period is <2 mL (for treatment time/method not considered as secondary variable)
- Time to onset of controlled bleeding. Onset of controlled bleeding is defined by the first day for which the menstrual blood loss for all subsequent 28-day periods up to the end of the treatment period is <80.00 mL (for treatment time/method not considered as secondary variable)

- Volume of menstrual blood loss per 28 days
- Volume of menstrual blood loss per bleeding episode for the first, second, and if applicable third bleeding episode after the EoT
- Volume of menstrual blood loss per bleeding episode within the treatment break. All days of the bleeding episodes will be used even if some days of the episode lie outside the treatment break.
- Percentage of subjects with 50% reduction in menstrual bleeding per 28 days compared to baseline
- Time to start of bleeding after last study drug intake (assessed by the UF-DBD in addition to the other two measurement methods). If bleeding has to be induced, the subject's data will be censored at that time point for the induction.

[...]

- Change in CGI\_I scores compared to baseline
- Change from baseline in hemoglobin, hematocrit, and ferritin
- Percentage of subjects with normal hemoglobin >12 g/dL and normal hematocrit >36%

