##### 10.3.1.1 Primary efficacy variable

*This section was changed in Amendment 1, see Section 15.1.1*

The primary efficacy variable is amenorrhea (yes/no), defined as MBL < 2 mL during the last 28 days of treatment.

If an endometrial biopsy was conducted during this time period, bleeding on the day of biopsy and the 3 days thereafter will not be considered in this evaluation.

For the primary analysis, the amenorrhea rates at the end of Treatment Period 1 of all Treatment Groups will be used.

Subjects who discontinue treatment prior to completion of treatment Week 8 of the respective treatment period will be considered not having amenorrhea.

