6.2 Efficacy

The following sections describe the efficacy analyses of primary, secondary, and other efficacy variables in detail. Further variables that were captured during the study will be either analyzed descriptively or displayed in subject listings.

The primary efficacy variable and secondary efficacy variables will be calculated based on the AH method. Other efficacy variables related to MBL will be calculated based on both the AH method and MP. If an endometrial biopsy was conducted during a time period for which bleeding will be assessed, bleeding or 'spotting' on the day of biopsy and the 3 days thereafter will not be considered in the derivation of any variables that belong to primary, secondary or other efficacy variables. Thus, prior to the assessment of bleeding variables, such as amenorrhea, for example, the AH and UF-DBD entries during those days will be set to 0 mL and "No vaginal bleeding", respectively.

For the confirmatory efficacy analysis, a hierarchical testing approach will be applied, involving the primary efficacy variable amenorrhea (yes/no) and the first three secondary efficacy variables HMB response, time to onset of amenorrhea, and time to onset of controlled bleeding. These tests always include a comparison of vilaprisan 2 mg versus placebo:

After 12 weeks of treatment in TP1:

Comparison of vilaprisan 2 mg in pooled treatment groups A1 and B2 (as the treatments are the same and pooling increases the power) vs. placebo in treatment group B1.

In total, four tests will be carried out each to an alpha level of 0.05, see also Figure 6–2: First, the test for the primary efficacy variable amenorrhea (yes/no) will be carried, followed by the test for HMB response (yes/no), the test for time to onset of amenorrhea, and finally, the test for onset of controlled bleeding. As the hierarchical testing procedure follows a fixed sequence, it stops as soon as any of these tests cannot be rejected to an alpha level of 0.05, and all further tests after failing to reject one null hypothesis in the testing sequence will be considered exploratory. This fixed sequence procedure accounts for the multiplicity created by carrying out multiple tests.

[figure not shown]

Figure 6–2: Hierarchical testing strategy for the confirmatory efficacy analysis

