- (b) If both, the bleeding intensity and the AH value, are missing for any of the last 28 days, the 28-day period will be extended: The left margin of the 28-day period will be displaced backwards in time and step-wise until the required number of 28 non-missing AH values are included. The left margin may be displaced backwards at maximum up to the end of the first bleeding episode when treatment was started in respective treatment period.

Considering this time window, a subject will be considered as not having amenorrhea if

- i) the sum of the non-missing (i.e. original or imputed) AH values is ≥ 2 mL, or
- ii) there is at least one day with missing AH value and bleeding intensity of 'mild' up to 'very severe' after having applied the imputation rules, or
- iii) the subject did not complete at least 8 weeks of treatment.

If neither of i), ii) or iii) applies, the subject will be considered as having amenorrhea.

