6.2.3.1 Binary bleeding variables

• Treatment success rate

The treatment success rate is defined as percentage of subjects who fulfill the criteria of HMB response (MBL <80.00 mL and >50% reduction in MBL as compared to baseline) and who have not been withdrawn from the study due to AEs, due to non-fulfillment of selection criteria (related to fibroid size or HMB at baseline), due to fibroid surgery having been performed during the study. Treatment success rate will be derived separately for the AH method and for MP.

Only fibroid surgeries that occur during the length of the originally planned study design (including FUP) prior to the temporary pause (Integrated Clinical Study Protocol, version 3.0, and protocol versions before) will be considered for deriving the treatment success rate. The FUP visit of the originally planned study design is on Day 7-15 of the 2nd menstrual cycle after the subject's end of treatment. That means that for subjects who have a prolonged FUP due to the temporary pause, the FUP according to the original study design will be derived. The derivation will be based on the end date of the subject's last treatment period and a follow-up time fixed to 12 weeks. Assuming a time to first menses after end of treatment of about 4 weeks and a cycle length of 4 weeks, 12 weeks of follow-up will cover at least the time period until the FUP visit would have been conducted according to the original study design.

Treatment success will be summarized with frequency tables by treatment period within treatment group. Number of observations and percentages will be presented.

• Amenorrhea

Amenorrhea, as further efficacy variable, is defined as MBL < 2 mL per 28 days of treatment for consecutive, non-overlapping 28-day periods not considered for the primary efficacy variable. An analogous approach as described for amenorrhea in the last 28 days of treatment (Section 6.2.1) will be applied to assess the amenorrhea status for each of the consecutive, non-overlapping 28-day periods within a treatment period (except for the 28-day period extension in case of missing values and criterion iii), which both do not apply).

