In case of no premature discontinuation, amenorrhea will be evaluated for the first and second 28-day periods of the subject's TP1 and TP2 when the AH method is used. When the MP is used, amenorrhea will be evaluated in all non-overlapping 28-day periods of TP1 and TP2. Only subjects with completed 28-day periods will be considered for the analysis of amenorrhea in those 28-day periods.

In addition, amenorrhea will be analyzed for an incomplete period which does not comprise 28 days. This analysis is based on all subjects for whom the length of the treatment period is not a multiple of 28 days. The reason for this might be premature discontinuation from the study or prolonged treatment.

Amenorrhea will be summarized by a frequency table by (pooled) treatment group and the 28-day periods grouped by treatment period.

• HMB response

HMB response, as further efficacy variable, is defined as MBL <80.00 mL per 28 days of treatment and >50% reduction from baseline where MBL is assessed for consecutive, non-overlapping 28-day periods not considered for the secondary efficacy variable. An analogous approach as described for HMB response in the last 28 days of treatment (Section 6.2.2) will be applied to assess HMB response for each of the consecutive, non-overlapping 28-day periods within a treatment period (except for the 28-day period extension in case of missing values and criterion ii), which both do not apply).

In case of no premature discontinuation, HMB response will be evaluated for the first and second 28-day periods of the subject's TP1 and TP2 when the AH method is used. When the MP is used, HMB response will be evaluated in all non-overlapping 28-day periods of TP1 and TP2. Only subjects with completed 28-day periods will be considered for the analysis of HMB response in those 28-day periods. In addition, HMB response will be analyzed for an incomplete period which does not comprise 28 days. This analysis is based on all subjects for whom the length of the treatment period is not a multiple of 28 days. The reason for this might be premature discontinuation from the study or prolonged treatment.

HMB response will be summarized by a frequency table by (pooled) treatment group and the 28-day periods grouped by treatment period.

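### End-of-period pictogram response rates leave out women who stopped early, while the alkaline hematin rates count stops before Week 8 as failures, so the two rates share no rule

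*Protocol*

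**What the plan says.** **AH, end of the treatment period.** Protocol 10.3.1.1 sets the rule for early stops: "Subjects who discontinue treatment prior to completion of treatment Week 8 of the respective treatment period will be considered not having amenorrhea". SAP 6.2.1 repeats it as criterion iii), which applies if "the subject did not complete at least 8 weeks of treatment". SAP 6.2.2 has the same criterion for HMB response. Both variables are analysed on the FAS. Where days are still missing after imputation, the 28-day window is extended backwards.

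**Pictogram.** Protocol 10.3.1.3 lists the variable as "Amenorrhea (yes/no), defined as MBL < 2 mL per 28 days of treatment (for treatment time/method not considered as primary variable". SAP 6.2 states: "Other efficacy variables related to MBL will be calculated based on both the AH method and MP". SAP 6.2.3.1 then adds: "When the MP is used, amenorrhea will be evaluated in all non-overlapping 28-day periods of TP1 and TP2". That includes Days 57–84. The derivation follows SAP 6.2.1 "except for the 28-day period extension in case of missing values and criterion iii), which both do not apply". The denominator is restricted: "Only subjects with completed 28-day periods will be considered for the analysis of amenorrhea in those 28-day periods". HMB response is handled in the same way. With AH, these per-period tables cover only the first and second 28-day periods.

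**Women with a part period.** SAP 6.2.3.1 also provides: "In addition, amenorrhea will be analyzed for an incomplete period which does not comprise 28 days". This row takes every woman whose treatment period is not a multiple of 28 days, whether she stopped early or was treated longer than planned.

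**The concern.** AH and the pictogram were both collected throughout the study, and a reader of the report will set their end-of-period rates side by side. Under the SAP these rates have different denominators and different failure rules. A gap between them could come from the rules and not from the measurements, and no planned table would let a reader separate the two. The AH sequence has the same break: periods 1 and 2 are in women who completed each period, and the end-of-period value is on the FAS.

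Neighbouring variables use other rules again. Diary-based absence of bleeding (SAP 6.2.2) keeps the 8-week rule and the extension. Blood-loss volume (SAP 6.2.3.3) uses women who entered the period. Pictogram treatment success (SAP 6.2.3.1) builds on HMB response but states neither a 28-day window nor a completer restriction.

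**Working it through.** **Step 1. The rules side by side**

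| Situation | AH, last 28 days of treatment (SAP 6.2.1, 6.2.2) | Pictogram, Days 57–84 (SAP 6.2.3.1) |
|---|---|---|
| Denominator | FAS | FAS women who completed the period |
| Randomized, never started for a reason other than the pause | In the FAS, failure | Not counted |
| Stop before Week 8 | Failure | Not counted |
| Stop in Weeks 8–12 | Scored on her last 28 treated days | Not counted |
| Treated beyond 84 days | Scored on her last 28 treated days | Scored on Days 57–84 |
| Days still missing after imputation | Window extended backwards | No extension |

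No AH row for Days 57–84 in completers is described, and no pictogram row for the last 28 days on the FAS. So no end-of-period pair of response rates shares a rule.

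**Step 2. Inputs.** The plan gives no figure for this gap, so there is none to reproduce. Protocol 10.4 supplies the planning values:
- Amenorrhea in ASTEROID 1 for US / Japan / European Union and Canada: about 0.7, 0.9, 0.9 on vilaprisan and 0.2, 0.0, 0.1 on placebo.
- Planned regional mix: 50%, 25%, 25%.
- Planned overall dropout: about 20%.

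Weighted rates: vilaprisan 0.5 × 0.7 + 0.25 × 0.9 + 0.25 × 0.9 = 0.80; placebo 0.5 × 0.2 + 0.25 × 0.0 + 0.25 × 0.1 = 0.125.

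Assumptions: these are the rates in women who continue, the two methods agree in every woman, and the share d stopping before Week 8 is equal across arms. The documents do not give d, so a range is shown.

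**Step 3. Stops before Week 8 only.** With p the rate in women who continue, AH rate = p × (1 − d), pictogram rate = p, and the gap is p × d.

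| d | AH vilaprisan / placebo / difference | Pictogram vilaprisan / placebo / difference | Gap in points: vilaprisan / placebo / difference |
|---|---|---|---|
| 5% | 0.76 / 0.119 / 0.641 | 0.80 / 0.125 / 0.675 | 4 / 0.6 / 3.4 |
| 10% | 0.72 / 0.1125 / 0.6075 | 0.80 / 0.125 / 0.675 | 8 / 1.25 / 6.75 |
| 20% | 0.64 / 0.10 / 0.54 | 0.80 / 0.125 / 0.675 | 16 / 2.5 / 13.5 |

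In planned numbers with d = 20%: of 2 × 52 = 104 women on vilaprisan in Treatment Period 1, 104 × 0.8 = 83.2 continue and 83.2 × 0.80 = 66.56 have amenorrhea. AH reports 66.56 / 104 = 0.64; the pictogram table reports 66.56 / 83.2 = 0.80.

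**Step 4. Stops in Weeks 8–12 only.** AH scores these women and the pictogram table drops them. If all 20% stop then, with rate q in their last 28 treated days, AH on vilaprisan = 0.8 × 0.80 + 0.2 × q = 0.64 + 0.2q. For q = 0, 0.4, 0.8 and 1 this gives 0.64, 0.72, 0.80 and 0.84, against 0.80 for the pictogram. Here AH can be the higher of the two.

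**Step 5. Under the fix.** With the AH rules applied to pictogram values, identical readings give identical rates. In the 20% row of Step 3, the pictogram would show 0.64 / 0.10 / 0.54.

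**The case against.** The strongest reply is that the SAP implements a separate variable, and legitimately. Protocol 10.3.1.3 defines it per 28 days of treatment, not for the last 28 days, and states no denominator. The 8-week rule in Protocol 10.3.1.1 and 10.3.3 is written for the primary variable and the secondary HMB response. For periods 1 and 2 an 8-week criterion has no meaning, and backward extension would make the periods overlap. All of this stands: the SAP does not contradict the Protocol, and a completed-period table is a fair display. It does not supply an end-of-period pictogram rate that can be read against AH.

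Early stoppers do appear in the incomplete-period row. That row does not return them to the Days 57–84 denominator as failures, it mixes them with women treated for longer than planned, and it misses a woman who stops exactly on Day 28 or Day 56.

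Comparable pictogram results also exist elsewhere: SAP 6.2.3.2 derives pictogram time to onset by reference to 6.2.2. That helps, but those are times to onset, not response rates.

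The consequence is limited. The per-period tables are descriptive frequency tables, no analysis of agreement between the methods is planned, and the Amendment 1 rationale (Protocol 15.1.1.1) treats the pictogram as not validated. These points limit the importance and leave the mismatch in place.

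A reader might infer that the two methods will differ through dropout alone. Step 1 shows that treatment beyond 84 days and missing diary days also separate them.

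**Conclusion.** The mismatch is real. Pictogram amenorrhea and HMB response at the end of a treatment period are completers' rates, the AH counterparts are FAS rates with stops before Week 8 as failures, and the two can differ when every reading agrees. Stops before Week 8 push the pictogram rate up, by 4–16 points on vilaprisan if 5–20% stop that early and 0.80 of those who continue have amenorrhea. The upper end is probably generous: 20% is the planned overall dropout for a study with two treatment periods, and SAP section 3 says women already in a treatment period at the pause were told to complete it.

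Two stronger readings are not supported. A reader might infer that the pictogram must look better than AH. Stops in Weeks 8–12 can reverse the sign (Step 4), and the net direction once longer treatment and missing days are added is not fixed by the documents. A reader might also infer a false drop in the AH course at the end of Treatment Period 1. Treatment starts during a bleed (Protocol 7.1), so period 1 should be low and the course should rise from it; any fall after period 2 depends on dropout timing that is not given.

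The four confirmatory tests, their alpha and the success criterion are unaffected. This is a cheap improvement to descriptive reporting.

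**What to change.** In SAP 6.2.3.1:
- Add pictogram amenorrhea and HMB response for the last 28 days of each treatment period on the FAS, with the rules of 6.2.1 and 6.2.2 including the 8-week criterion and the window extension. Show them beside the AH result.
- Keep the per-period tables as supportive, labelled as women who completed the period, with denominators shown.
- Add an AH row for Days 57–84 to those tables, so that all three periods and both methods follow one rule there.

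Cost: an existing derivation run on pictogram values, plus one table row. Pictogram rates will probably look somewhat less favourable. The confirmatory analysis does not change.
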